7.7. UNSCHEDULED VISITS

Unscheduled visits in symptomatic subjects (subjects with symptoms of reduced leaflet function) and any other subjects needing a study related follow-up visit that is not covered by the standard visit schedule. The following items may be captured:

- Subject status
- Physical evaluation (including cardiac rhythm and NYHA functional classification)
- Medications
- Transthoracic echocardiogram (TTE) (if available)
- SAEs

7.8. 2ND CT SCAN VISIT/REDUCED LEAFLET VISIT (AFTER THE 1ST CT SCAN, BUT PRIOR TO 1-YEAR FOLLOW-UP VISIT)

This visit is intended provide a 2nd follow-up 4D CT scan if the 1st CT scan showed reduced leaflet motion. This second CT scan visit is expected at approximately 6-10 months, but prior to 1 year follow-up. This follow-up evaluation shall be conducted in an office, hospital or clinic setting by the PI or his/her designee, at a time designated by the PI.

If the 1st CT scan showed no signs of reduced leaflet motion, a repeat 4D CT is not mandated and will only be done if it becomes clinically indicated. For subjects unable to undergo a contrast CT scan (e.g. inadequate renal function), a TEE may be performed.

The following data listed below shall be collected if this visit is required:

- Subject status
- Physical evaluation (including cardiac rhythm and NYHA functional classification)
- Medications

- Hemodynamic data from TTE examination measured at investigational site (MPG; PPG, EOA, aortic regurgitation with severity and location)
- CT scan with contrast
- TEE only in subjects that are unable to undergo CT scan at the time of follow-up
- Medications
- SAEs

7.9. 1-YEAR FOLLOW-UP VISIT

This visit is intended as a clinic visit at 1 year \pm 1 month after the day of the surgery. Follow-up evaluations shall be conducted in an office, hospital or clinic setting and are to be performed by the PI or his/her designee. **All efforts should be made to ensure that the subject comes to the clinic.**

The following data listed below shall be collected:

- Subject status
- Physical evaluation (including cardiac rhythm and NYHA functional classification)
- Medications
- Hemodynamic data from TTE examination measured at investigational site (MPG; PPG, EOA, aortic regurgitation with severity and location)
- Medications
- SAEs

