8.2. HANDLING OF STUDY DISCONTINUATIONS

8.2.1. Handling of Subject Temporary Treatment Discontinuation or Termination

For all subjects reaching the end of the study (completed 1 year visit, death, or explants) or in case of premature withdrawal as described in Section 6.3.5 (lost-to-follow-up, or subject's decision) a study termination form will be filled out in order to document the date and reason for discontinuation.

Every attempt must be made to have all subjects complete the follow-up visit schedule. A subject will be considered lost to follow-up when all efforts to obtain information are unsuccessful. At a minimum, the effort to obtain information must include at least two (2) attempts to make contact via phone, and a certified letter should be sent to the subject's last known address. Both phone contacts and copy of the letter must be documented/available in the subject's medical record and recorded in the eCRF. For subjects discontinued by the PI for a safety reason, the PI shall document the reasons for the decision.

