4 OVERVIEW OF PLANNED STATISTICAL ANALYSIS

4.1 MAIN STATISTICAL ANALYSIS

Main statistical analysis will be performed after all evaluable subjects have completed the first CT scan at expected 1-6 months post-implant.

Study: APR002 BELIEVE

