5.2 DESCRIPTIVE STATISTICS

Descriptive statistics will be calculated using as reference the number of subjects in the relevant analysis population (any exception will be specified) according to the nature of the data as follows:

Study: APR002 BELIEVE

- Continuous variables: number of non-missing observations, arithmetic mean, standard deviation, minimum and maximum values, median and quartiles.
 - If there are less than 5 observations, only the number of non-missing observations, arithmetic mean, median, minimum and maximum will be presented.
- Categorical variables: number of non-missing observations (n), the number of missing and the relevant percentage on the analysis population, number and relative frequencies. If not defined otherwise, the percentage denominator will be the number of subjects with nonmissing information.
 - In case of subcategories, the relative frequencies will be calculated based on the subjects in the subcategory, in this case a footnote will be added explaining the different denominators.
- Time-to-event variables: number of non-missing observations (n), minimum, first quartile, median including 90% CI, third quartile, and maximum. For calculating the survival estimate 90% CI bounds the log-log transformed estimate of CI bounds will be used. Greenwood formula will be used to estimate the variance of the log-log transformation of the Kaplan-Maier estimator.

In addition, Kaplan-Meier estimates and plots will be provided with:

- o the respective number at risk and the Kaplan-Meier estimates at time points 1 month, 3 months, 6 months, 9 months and 1 year.
- o the median and its 90% Cl.
- o the Hazard Ratio (HR), its 90% CI and the relevant p-value, when applicable.

Subjects ongoing and who are free from event at the analysis cut-off date will be censored at the analysis cut-off date. Subjects who have discontinued without an event will be censored at the date of discontinuation.

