11.5 Freedom from Valve Safety

The following mortality and morbidity outcomes will be analyzed by means of time to event methods:

all-cause mortality

COPYRIGHT LIVANOVA. ALL RIGHTS RESERVED. MAY NOT BE REPRODUCED WITHOUT PERMISSION. ALL HARD COPIES SHOULD BE CHECKED AGAINST THE CURRENT ELECTRONIC VERSION WITHIN MASTERCONTROL PRIOR TO USE AND DESTROYED PROMPTLY THEREAFTER. ALL HARD COPIES ARE CONSIDERED UNCONTROLLED DOCUMENTS.

LN-GLB-CLN-TEM-0033 rev1 Page 21 of 42

- valve re-intervention
- myocardial infarction
- structural valve deterioration
- moderate or severe valve regurgitation
- valve endocarditis
- valve thrombosis
- thromboembolic events
- hemolysis
- major bleeding
- pacemaker implantation

Cox's proportional hazards regression models (Cox 1972, Breslow 1975) will be performed including, one by one, the following covariates: age class [refers to "≥18 and <65" years], gender [refers to "male"], ethnicity [refers to "not Hispanic or Latino"], presence of subject risk factor at baseline [refers to "No"], , NYHA at baseline [refers to "Class I"], abnormality of ascending aorta or of aortic root at implant [refers to "No"], presence of aortic regurgitation measured by post-implant intraoperative TEE [refers to "No"], reduced leaflet motion at first CT scan [refers to "No"], including the subgroup defined in Section 5.3: concomitant procedures [refers to "without"], subject symptoms [refers to "asymptomatic"], ACT/DATP [refers to "off"], Core Lab evaluation [refers to "TEE"].

Study: APR002 BELIEVE

Hazard rate, and its 90% CI, will be reported for each covariate.

Proportional hazard assumption will be investigated for each time-dependent outcome. In case of non-proportional hazards, a Weibull model will be assumed as parametric form of the distribution of survival times.

An additional analysis will be performed in order to evaluate the time free from ACT/DAPT to primary endpoint (reduced leaflet motion) up 1 year post-implant. Kaplan-Meier estimates and plots of time to event after implant will be produced as in Section 5.2. Subjects will be included in the analysis starting from their stop date of ACT/DAPT until the first evaluation of leaflet motion.

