ENR population	 SCR flag= "Yes" and DXSTDAT2 not missing ("Implant Surgical Details" e-CRF) and existing Enrolled Date
SAF population	 ENR flag= "Yes", and DXPERF= "Yes" ("Implant Surgical Details" e-CRF)
PP population	As reported in the Believe Risk Based Study Management Plan.
Time to study	"Implant Surgical Details" e-CRF and "Study Termination" e-CRF
termination (months)	[DSSTDAT – DXSTDAT2 + 1] / 30.4375

COPYRIGHT LIVANOVA. ALL RIGHTS RESERVED. MAY NOT BE REPRODUCED WITHOUT PERMISSION. ALL HARD COPIES SHOULD BE CHECKED AGAINST THE CURRENT ELECTRONIC VERSION WITHIN MASTERCONTROL PRIOR TO USE AND DESTROYED PROMPTLY THEREAFTER. ALL HARD COPIES ARE CONSIDERED UNCONTROLLED DOCUMENTS.

LN-GLB-CLN-TEM-0033 rev1 Page 40 of 42

Time to event	"Implant Surgical Details" e-CRF
(months)	[Even date – DXSTDAT2 + 1] / 30.4375 Subjects ongoing and who are free from event at the analysis cutoff date will be censored at the analysis cut-off date. Subjects who have discontinued without an event will be censored at the date of discontinuation.
Age at Enrollment (years)	"Demographics" e-CRF and "Inclusion/Exclusion Criteria" e-CRF Age= [ICFDAT - BRTHDAT + 1]/365.25 As only month and year of birth are reported in the CRF, 1 st day of the month will be used for birth date.
Change from baseline	Test Value at Visit X - Baseline Value

Where

ACTDIDAT = "Date Subject Discontinued ACT/DAPT Therapy"

BRTHDAT= "Date of Birth"

CPAETERM= "Complications/Please specify if any of the following intraoperative complications occurred. /AE Term"

CPYN= "Was concomitant procedure performed?"

DIMODEL= "Valve Model"

DSDECOD= "Reason for Termination"

DSSTDAT= "Date of Study Termination"

DVDECOD= "Deviation Description"

DVICSPEC= "If Informed Consent, specify reason"

DXPERF= "Was the implant successful?"

DXSTDAT2 = "Date of Implant"

ICFDAT = "Informed Consent Date"

IEYN= "Met All Eligibility Criteria?"

COPYRIGHT LIVANOVA. ALL RIGHTS RESERVED. MAY NOT BE REPRODUCED WITHOUT PERMISSION. ALL HARD COPIES SHOULD BE CHECKED AGAINST THE CURRENT ELECTRONIC VERSION WITHIN MASTERCONTROL PRIOR TO USE AND DESTROYED PROMPTLY THEREAFTER. ALL HARD COPIES ARE CONSIDERED UNCONTROLLED DOCUMENTS.

LN-GLB-CLN-TEM-0033 rev1 Page 41 of 42

IMGTYPE= "Specify the imaging modality currently being used for the subject"

MHCVDAT = "If Myocardial Infarction, date"

MHSTDAT3= "If Stroke, date"

NY= "No/Yes"

SCDISCYN= "Was the subject discharged on anticoagulant and/or dual platelet therapy?"

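### Event-free subjects lost to follow-up are censored at discontinuation rather than at last known status, so 1-year freedom from valve safety events can be overstated

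*SAP*

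**What the plan says.** SAP 5.2 gives the rule for subjects still in the study: "Subjects ongoing and who are free from event at the analysis cut-off date will be censored at the analysis cut-off date". For those who have left, SAP 5.2 and the time-to-event row of SAP 18.13 say: "Subjects who have discontinued without an event will be censored at the date of discontinuation". Neither place refers to last contact, last visit or last known status, and no status check at the cut-off is required.

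The discontinuation date comes from Protocol 8.2.1, where "a study termination form will be filled out in order to document the date and reason for discontinuation". The same section says: "A subject will be considered lost to follow-up when all efforts to obtain information are unsuccessful". It asks for at least two phone calls and a certified letter, and gives no deadline.

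The rule feeds SAP 11.5, which opens: "The following mortality and morbidity outcomes will be analyzed by means of time to event methods". SAP 5.2 asks for "the respective number at risk and the Kaplan-Meier estimates at time points 1 month, 3 months, 6 months, 9 months and 1 year". These serve the secondary endpoint on freedom from valve safety events (Protocol 6.3.6).

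On timing, Protocol 7.8 says that after a normal first CT "a repeat 4D CT is not mandated and will only be done if it becomes clinically indicated". SAP 4.1 says: "Main statistical analysis will be performed after all evaluable subjects have completed the first CT scan". The final analysis (SAP 4.2) waits until every subject has finished the study.

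**The concern.** Kaplan-Meier estimation assumes that a subject counted as at risk would be seen to have the event if it happened. For a lost subject this stops being true at the last contact. If the termination form carries a later date, that subject stays in the risk set while unable to contribute an event. The denominator is too large, and freedom from death, thrombosis, thromboembolism, bleeding and the other listed outcomes reads too high.

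The schedule leaves room for a long gap. A subject with a normal first CT has no scheduled visit until the 1-year window, so a loss of contact may first be noticed then. Late subject-years in SAP 13.1.2 have no stated end date. If they run to the same dates, the linearized rates are diluted too.

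**Working it through.** **The plan's own figure.** The documents state no figure for the safety time-to-event analysis. The one design figure reproduces: with 7 of 75 the exact 90% interval is 4.46% to 16.82%, width 12.35%, below the stated 13%; and 75/0.85 = 88.2, against approximately 88 stated. It does not depend on censoring.

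**Length of the gap** (Protocol 7.10 and the schedule table in 8.1; 1-year visit on days 335 to 395)
- Discharged off ACT/DAPT: discharge on day 0 to 30 and first CT 30 to 90 days later, so day 30 to 120. Gap: 335 − 120 = 215 to 395 − 30 = 365 days.
- ACT/DAPT stopped at the preferred day 90: first CT 30 to 90 days later, day 120 to 180. Gap: 335 − 180 = 155 to 395 − 120 = 275 days. The guide in 7.10 prints 60 to 240 days after discontinuation for this group, which would allow shorter gaps.

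**Simple case.** Assume 13 of 88 are lost early and closed at or after 12 months, with k events among the other 75, all after that contact. One-year freedom is 1 − k/88 under the SAP rule and 1 − k/75 with last-contact censoring. For k = 4: 95.5% against 94.7%. For k = 7: 92.0% against 90.7%.

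**Dependence on the assumptions.** Assumed: true 1-year risk p = 7%, constant hazard from day 31 to 365 (334 days), and last contact of lost subjects spread over days 40 to 180 (mean 110). A lost subject is then observed for f = (110 − 31)/334 = 0.237 of the late period. For small p and closure at day 395 with m lost, the estimate is roughly p × [(88 − m) + m·f]/88.

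| Scenario | Arithmetic | Simulation |
|---|---|---|
| 13 lost, closed day 395 | 7% × (75 + 3.07)/88 = 6.2% | 6.2% |
| 4 lost, closed day 395 | 7% × (84 + 0.95)/88 = 6.8% | 6.7% |
| 13 lost, closed 30 to 90 days after contact | unobserved 13 × 60 = 780 of 75 × 334 + 13 × 139 = 26,857 counted days, 2.9%; 7% × 0.971 = 6.8% | 6.9% |
| None lost | 7.0% | no bias |

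Arithmetic and simulation agree to about 0.1 point. In the first scenario last-contact censoring returns 7.0%. A true 20% becomes 17.7% under the SAP rule and 19.9% with last contact. If lost subjects have three times the hazard, a true 8.9% is estimated as 6.7%, or 7.5% with last contact.

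**Late subject-years**, if they run to the same dates: the first scenario adds 13 × (395 − 110)/365.25 = 10.1 subject-years to about (75 × 334 + 13 × 79)/365.25 = 71.4 (events ignored), or 14%.

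**Analyses with subjects ongoing.** These were simulated with 24-month uniform accrual.
- 15% lost, true risk 10%, no between-visit reporting: SAP rule 7.8%; truncating both events and event-free time at the last visit, 10.1%. With full reporting for subjects not lost, the SAP rule gives 8.9%.
- None lost, full reporting, cut-off 6 months after accrual ends, true risk 7%: SAP rule 7.0%. Truncating only the event-free subjects while still counting later reported events gives 8.0%.

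**The case against.** A reader might infer that every month between the first CT and the 1-year visit is unobserved time credited as event-free. The documents do not support that. The 1-year visit collects SAEs (Protocol 7.9), sites report within 10 days of awareness and the reporting table includes a 6-to-9-month period (12.1), and the sponsor collects SAEs until participation ends (13.2). For subjects who attend at 1 year the gap is covered retrospectively. The cut-off sentence also has no role at the final analysis, which is the basis for the study report.

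Nor do the documents support reading the 15% attrition as loss to follow-up. Protocol 4.4 and 10.2 define it as the shortfall from enrolled subjects to evaluable CT scans, which can include unreadable scans. Closure at day 395 is likewise an assumption: Protocol 8.2.1 sets no timing, and the time-to-event row of SAP 18.13 does not name the study-termination field. A subject who withdraws in person would normally have a discontinuation date that is itself a contact.

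It is also tempting to say that any error must favour the device and that last-contact censoring removes it. With full between-visit reporting and no loss, the SAP's cut-off rule is unbiased, and a careless last-visit rule biases upward (8.0% against a true 7%).

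All of this stands and limits the size. It does not remove the defect for lost subjects: a site cannot report events in someone it cannot reach, and no passage ties their censoring to last known status.

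**Conclusion.** The point holds for subjects lost to follow-up, and for subjects still ongoing when the main analysis or an internal evaluation (SAP 4.3) is run. At the final analysis only the lost subjects matter. At an assumed true 7% risk the understatement runs from zero with none lost to about 0.8 percentage points with 13 of 88 lost and closed on day 395. The scenarios with fewer losses or prompt closure come within 0.1 to 0.3 points of the truth. Even 0.8 points is under one-third of the estimate's standard error, which is roughly √(0.07 × 0.93/88) = 2.7 points.

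These sizes rest on assumed event risk, number lost, timing of last contact and closing delay, none of which the documents give. The effect on linearized rates is conditional, because SAP 13.1.2 does not say when late subject-years end. The primary endpoint proportion and the 75/88 calculation are unaffected. The affected outcomes are secondary, in a study that Protocol 10 describes as descriptive. Minor to moderate.

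**What to change.** In SAP 5.2 and 18.13:

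- Censor event-free lost subjects at the last date their event status was documented by visit, contact or record check. For death, use the last date known alive. Do not use the termination date.
- End late subject-years in SAP 13.1.2 on the same date.
- For analyses run while subjects are ongoing, choose one of two rules. Either confirm every ongoing subject's status at the cut-off and keep cut-off censoring, or truncate both events and event-free time at the last status date. Do not count later spontaneously reported events while truncating only the event-free subjects.
- State the censoring date for subjects who complete the 1-year visit, who are neither ongoing nor discontinued under the present wording.

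The cost is SAP wording and one derived date. SAP 18.13 already falls back on the last available visit date when it defines implant procedure completers, so the derivation is feasible. Confirming status at the cut-off would need a contact round at the sites. Subject-years fall slightly and intervals widen slightly. The change does not correct for lost subjects being sicker, so the report should also give the number lost and the interval from last contact to termination.

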5.3 SUBGROUPS DEFINITIONS

The following subgroups will be defined:

- Concomitant Procedures (at implant):
 - Subject implanted with a concomitant procedure performed.
 - Subject implanted without a concomitant procedure performed.
- Subject symptoms (at first/second CT scan, as appropriate):
 - Asymptomatic
 - Symptomatic
- ACT/DATP (at hospital discharge):

COPYRIGHT LIVANOVA. ALL RIGHTS RESERVED. MAY NOT BE REPRODUCED WITHOUT PERMISSION. ALL HARD COPIES SHOULD BE CHECKED AGAINST THE CURRENT ELECTRONIC VERSION WITHIN MASTERCONTROL PRIOR TO USE AND DESTROYED PROMPTLY THEREAFTER. ALL HARD COPIES ARE CONSIDERED UNCONTROLLED DOCUMENTS.

LN-GLB-CLN-TEM-0033 rev1 Page 9 of 42

- Subject on ACT/DAPT at hospital discharge (or 30-days after implant)
- Subject off ACT/DAPT at hospital discharge (or 30-days after implant)
- Core Lab evaluation (at first/second CT scan, as appropriate) by:
 - o CT scan
 - Transesophageal Echocardiogram (TEE)

5.4 DEFINITIONS

Investigational Device (ID)	PERCEVAL (PMA P150011)
Baseline	Last non-missing observation (scheduled or unscheduled) before implant.
	Measurements collected the day of implant, in absence of other time information, are considered baseline data.
	If a subject is missing the planned baseline collection, the previous non-missing evaluation will become the baseline value.
	If any observation will be available before or on the day of implant, an unscheduled assessment done before the discharged visit can be used as baseline.
Study Day Count	The day of implant is defined as study Day 1.
	Calculate the study day according to the following rules:
	If date < study Day 1 then study day = Date – study Day 1
	If date ≥ study Day 1 then study day = Date – study Day 1 +1

LN-GLB-CLN-TEM-0033 rev1 Page 10 of 42

Study phases	
Pre-implant (Screening)	Screening and pre-implant assessments, where informed consent is signed and eligible criteria are met, before subjects will be considered enrolled in the study.
Implant (Enrollment)	During the implant until the establishment of a successful procedure.
Hospital Discharge	Before the subject is discharged or within 30 days of implant.
ACT/DAPT discontinua- tion visit	Visit required only for subjects on ACT/DAPT at hospital discharge: from 1 to 6 months (3 months preferred) postimplant.
Follow-up evaluations: First CT scan	Minimum of 30 days (+ 60 days) after discharge or discontinuation of ACT/DAPT (expected from 1 to 6 months post-implant).
Second CT scan	For subject with reduced leaflet motion previously detected by Core Lab; after the 1^{st} CT scan, but prior to 1 year follow-up visit (expected from 6 to 10 months post-implant).
1 year	Clinic visit at 1 year ± 1 month after the day of the implant.
Pre-implant period	Period from signing of the informed consent until the day before the implant.
Post-implant period	Period from successful implantation of Perceval bioprosthetic heart valve to 30-days after hospital discharge visit (for subjects discharged off ACT/DAPT) or ACT/DAPT discontinuation visit (for subjects discharged on ACT/DAPT).
Post-ACT/DAPT period	Period from 31 st day after the hospital discharge (for subjects discharged off ACT/DAPT) or 1 st day after the ACT/DAPT discontinuation (for subjects discharged on ACT/DAPT) to 1 year visit.
Pooling of sites and countries	Unless otherwise specified, data from all of the study sites and countries will be pooled and the analysis performed on the complete database including subjects from all sites and countries.
Screening Failure	Subjects who are screened, informed consent was obtained, and not included in the study due to eligible criteria not met.
Implant procedure completers	Subjects successfully implanted who complete the post-implant period, namely who discontinued the ACT/DAPT at minimum 30 days.

COPYRIGHT LIVANOVA. ALL RIGHTS RESERVED. MAY NOT BE REPRODUCED WITHOUT PERMISSION. ALL HARD COPIES SHOULD BE CHECKED AGAINST THE CURRENT ELECTRONIC VERSION WITHIN MASTERCONTROL PRIOR TO USE AND DESTROYED PROMPTLY THEREAFTER. ALL HARD COPIES ARE CONSIDERED UNCONTROLLED DOCUMENTS.

LN-GLB-CLN-TEM-0033 rev1 Page 11 of 42

Study completers

Subjects who complete the 1 year visit.

Study: APR002 BELIEVE

6 Analysis population

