11.6 New York Heart Association (NYHA) classification

Subject improvement after valve implant will be determined by the McNemar-Bowker (extension of McNemar test to more than two categories) to test, at 90% two-side significance level, the marginal homogeneity between pre-operative and post-operative NYHA proportions. Besides, the NYHA classification will be summarized in a shift table by overall and, for the appropriate visits, by subgroup defined in Section 5.3.

Evaluation performed in corresponding of first and second CT scan visits will be displayed also categorizing by subject with/without reduction leaflet motion and within each leaflet motion category (normal, mildly reduced, moderately reduced, severely reduced and immobile). Number of non-missing observations (n) and percentage on the SAF population will be displayed.

Study: APR002 BELIEVE

A bar plot will be provided to graphically display the overall NYHA marginal percentages, by visit.

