18.2 Presentation of differences and changes

For changes from baseline, the later value will constitute the minuend and the baseline value the subtrahend. Changes will be calculated only for subjects with values at both considered visits.

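### The SAP 5.4 baseline definition ends by admitting an unscheduled assessment made after implant and before discharge, which contradicts its own first line

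*SAP*

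**What the plan says.** The baseline entry in SAP 5.4 has four parts:

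1. The main rule: "Last non-missing observation (scheduled or unscheduled) before implant".
2. An implant-day rule: "Measurements collected the day of implant, in absence of other time information, are considered baseline data".
3. If the planned baseline collection is missing, the previous non-missing evaluation is used.
4. A fallback. Its condition is "If any observation will be available before or on the day of implant", and its consequence is that "an unscheduled assessment done before the discharged visit can be used as baseline".

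Change from baseline is defined only in general terms. SAP 18.2 states: "For changes from baseline, the later value will constitute the minuend and the baseline value the subtrahend". It adds: "Changes will be calculated only for subjects with values at both considered visits". SAP 18.13 gives the derivation as "Test Value at Visit X - Baseline Value".

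SAP 8.3 shows baseline NYHA class and TTE hemodynamics next to the later assessments. SAP 11.6 tests marginal homogeneity "between pre-operative and post-operative NYHA proportions" and adds a shift table. SAP 11.5 and 10.5 use NYHA at baseline as a covariate.

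**The concern.** A baseline in a valve study should describe the patient before the valve is replaced. Part 4 of the definition can apply that label to an assessment made days after surgery. For gradients, orifice area and regurgitation, such a value already reflects the new valve. For NYHA it reflects early recovery from open surgery.

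The condition makes this worse. As written, the fallback is triggered when a valid baseline exists, which conflicts with part 1. A programmer cannot implement all four parts as they stand without deciding what the last one means. At stake are the meaning of the baseline column and of whatever is computed from it.

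**Working it through.** **The plan's own figures.** The only sizing figures are 75 evaluable scans, an exact two-sided 90% CI narrower than 13% when the sample proportion is below 10%, and about 88 enrolled (Protocol 10.2, SAP 2.3). Clopper-Pearson limits for 7/75 (9.33%) are 4.46% to 16.82%, a width of 12.35%. For enrollment, 75 / (1 − 0.15) = 88.2. Both agree with the plan, and neither uses a baseline value.

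**What the fallback adds.**
- Part 1 takes any value before implant, scheduled or unscheduled.
- Part 2 takes untimed values on the implant day.
- The only unscheduled pre-discharge assessments left for part 4 are those made after implant.
- If *any* is read literally, such a value may displace a true pre-implant value. If it is read as *no*, the value fills a gap. On both readings a post-implant value may be called baseline.

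**Part 2 has a related gap.** Some implant-day measurements are made with the new valve in place: SAP 11.5 refers to a post-implant intraoperative TEE, and SAP 8.2 to post-operative rhythm. An untimed value of this kind counts as baseline under part 2.

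**Where the baseline value goes.**

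| Output | Exposed? |
|---|---|
| Baseline NYHA and TTE presentation (SAP 8.3) | Yes |
| Any change derived under SAP 18.2 and 18.13 | Yes, if one is produced |
| Regurgitation shift tables (SAP 12.2.2) | Only if they start at baseline; the text does not say |
| Baseline NYHA covariate in Cox models (SAP 11.5) | Yes |
| Baseline NYHA covariate in multiple imputation (SAP 10.5) | Yes in the full model; the restricted model omits it |
| NYHA pre/post test (SAP 11.6) | Only if pre-operative class is filled from the 5.4 variable |
| Core Lab hemodynamics by visit (SAP 12.2.1) | Actual values; no change analysis is named |
| Primary CT proportion and its CI (SAP 10.4) | No |

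**Possible size, for illustration only.** The documents do not give k, the number of subjects who would take a post-implant baseline. Assume that a mean change is derived for all 88, that the true mean change is the same in affected and unaffected subjects, and that the substitute value already holds a share s of the implant effect. The derived mean change is then the true one multiplied by 1 − s × k/88.

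| k of 88 | s = 1 | s = 0.5 |
|---|---|---|
| 1 | 0.989 | 0.994 |
| 4 | 0.955 | 0.977 |
| 9 | 0.898 | 0.949 |
| 18 | 0.795 | 0.898 |

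With s = 1, the mean change shrinks by 1.1% (k = 1) to 20.5% (k = 18). This suits a variable such as a pressure gradient. It does not carry over to NYHA, where the share could be negative.

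**The case against.** The strongest reply is that little depends on this line. A reader might infer that the reported hemodynamic and NYHA improvement would be systematically too small. The documents do not support that:

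- SAP 12.2.1 analyzes Core Lab hemodynamics as actual values at each visit. SAP 18.2 and 18.13 say how a change would be computed, not that one is planned for gradients or orifice area.
- SAP 11.6 speaks of pre-operative class, not baseline. Protocol 7.2 and 7.3 collect it for all subjects, and the footnote to the schedule of procedures takes it from pre-implant history. It should rarely be missing.
- NYHA class a few days after open surgery may be better or worse than before, so a substituted value could shrink or enlarge the apparent improvement.

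A reader might also infer from the literal *any* that valid pre-implant values would routinely be overwritten. That reading would contradict part 1 and leave the fallback without a purpose, and the line is permissive rather than mandatory. *No* is very likely what was meant. A subject then needs both no value before or on the implant day and an unscheduled assessment before discharge, which should be uncommon.

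These points stand, and they limit the consequence. They do not remove the defect: on the sensible reading the fallback still labels a post-treatment value as baseline, and SAP 8.3, 11.5 and 10.5 use that label directly. Missing pre-implant data are also plausible, because consent may follow implant (Protocol 6.3.4) and preoperative data are then gathered afterwards. In addition, the pre-implant TTE is not sent to the Core Lab, while an unscheduled echo may be (Protocol 6.3.7). The SAP does not say whether baseline hemodynamics come from the site or the Core Lab. If only Core Lab readings were used, the condition of no earlier value would hold more widely for TTE.

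**Conclusion.** The contradiction within SAP 5.4 is real and does not depend on how the faulty condition is read. It is a minor point. It could distort the baseline presentation, any derived change, possibly the regurgitation shift tables, and the baseline NYHA covariate in the Cox models and in one sensitivity analysis. It reaches the NYHA pre/post test only through a programming choice that the SAP does not state. The primary CT analysis and the sample size are untouched.

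The number of subjects affected is not given. The judgment that it is small rests on pre-implant values being collected as Protocol 7.3 requires, on baseline hemodynamics not being restricted to Core Lab readings, and on unscheduled pre-discharge assessments being uncommon. The direction of bias is likely toward a smaller change for gradients, if a change is derived, and is unknown for NYHA.

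**What to change.** - Delete the last sentence of the baseline definition in SAP 5.4.
- Define baseline as the last value known to precede implant. If there is none, baseline is missing and appears in the missing count. This agrees with SAP 18.5, which does not impute unless stated, and with the SAP 18.2 rule that both values are needed for a change.
- Flag or list subjects whose baseline is an untimed implant-day value, since deleting the last sentence alone leaves that route open.
- State in SAP 11.6 that pre-operative NYHA means the pre-implant value.
- It would also help to say whether baseline hemodynamics come from site or Core Lab readings, and whether the regurgitation shift tables start at baseline.

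The cost is a few lines of text and the loss of a baseline or change value for a few subjects. A subject with no baseline NYHA would drop out of the Cox model for that covariate, and SAP 10.5 would need one sentence on how the imputation model handles the gap.
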